 - AEs, absolute and change from baseline in clinical safety laboratory tests (estradiol for girls, LH, FSH), Tanner staging, ECG, and effects on menstrual cycle, vital signs, height, weight, and ECG parameters will be summarized, and observed potentially clinically significant (PCS) safety laboratory test values will be flagged and summarized. GBI scores (using the 10-item mania subscale), and C-SSRS scores will be summarized using descriptive statistics.
 - AEs and other safety endpoints will be reported separately for the 12-week open-label period and the 26-week double-blind period.
- Patient disposition and demographics will be summarized using descriptive statistics.

Testing Strategy

[figure not shown]
Not applicable

Sample Size Considerations

The calculation of power is based on a log-rank test for the time to relapse at a one-sided 5% level of significance using SAS® Proc Power. A sample size of 80 randomized patients (40 patients per treatment group) will provide at least 80% power to find a difference between vortioxetine and placebo as statistically significant, when expecting cumulative relapse rates at 0.42 and 0.69 over 26 weeks, respectively, corresponding to a hazard-ratio of 2.15.

It is anticipated that approximately 60% of *de novo* patients enrolled into the open-label period will qualify for the double-blind study period. One-hundred fifty (150) patients are estimated to be enrolled into the study (depending on number and randomization rate of *de novo* and rollover patients).

Panel 1 Study Design

* Patients in remission (CDRS total score ≤ 28) at the two last visits in the open-label treatment period / Study 12712A OR with an adequate clinical response ($\geq 50\%$ reduction in the CDRS-R total score compared to the baseline score and a CDRS-R total score ≤ 35) at the two last visits in the open-label treatment period

**Relapse: CDRS-R total score of ≥ 40 with a history of 2 weeks of clinical deterioration, or a clinical deterioration that in the investigator's opinion warrants alteration of treatment to prevent full relapse

Panel 2 Study Procedures and Assessments – Open-label Period for *de novo* Patients and Rollover Patients from Study 12709A

Visit Name	Open-label Period								Randomization	Withdrawal ^d	Safety Follow-up ^e
	Screening ^a only de novo	Baseline ^b de novo	Baseline ^c 12709A rollover	3	4	5	6	7			
Visit Number	1	2	2	3	4	5	6	7	8		
Day/End of Week	d-5/d-15	0	0	W1	W2	W4	W8	W10	W12		W16

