
Safety Objectives
 
 to evaluate long-term safety and tolerability of vortioxetine in paediatric patients with MDD 	
Safety Endpoints
 
 adverse events absolute values and changes from baseline in clinical safety laboratory test values (including estradiol [girls only], and luteinising hormone [LH], follicle-stimulating hormone [FSH]), vital signs, height, weight, Tanner staging, electrocardiogram (ECG) parameter values. Effects on menstrual cycle will be assessed. potentially clinically significant clinical safety laboratory test values, vital signs, weight changes, and ECG parameter values Columbia-Suicide Severity Rating Scale (C-SSRS) score General Behaviour Inventory (GBI) using the 10-item mania subscale (parental version)

3 Study Design

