16.8.8 Safety Analyses

The safety analyses will be based on the APES and the FAS.

All safety endpoints will be reported for the 12-week open-label period and the 26-week double-blind period separately.

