16.8.10 Analysis of Other Safety Endpoints

Absolute and change from baseline in clinical safety laboratory tests (estradiol for girls, LH, FSH), Tanner staging, and effects on menstrual cycle, vital signs, height, weight, BMI and ECG parameters will be summarized by treatment group. Potentially clinically significant (PCS) safety laboratory test values will be flagged and summarized.

GBI scores (using the 10-item mania subscale), and C-SSRS scores will be summarized using descriptive statistics.

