
Safety Objectives
 
• to evaluate long-term safety and tolerability of vortioxetine in paediatric patients with MDD	
Safety Endpoints
 
• adverse events• absolute values and changes from baseline in clinical safety laboratory test values (including estradiol [girls only], and luteinising hormone [LH], follicle-stimulating hormone [FSH]), vital signs, height, weight, Tanner staging, electrocardiogram (ECG) parameter values. Effects on menstrual cycle will be assessed.• potentially clinically significant clinical safety laboratory test values, vital signs, weight changes, and ECG parameter values• Columbia-Suicide Severity Rating Scale (C-SSRS) score• General Behaviour Inventory (GBI) using the 10-item mania subscale (parental version)

3 Study Design

This is an interventional, multi-national, multi-site, randomized, parallel-group, placebo-controlled, relapse-prevention study in paediatric patients with MDD from 7 to 11 years of age.

The study consists of a 12-week, open-label, flexible-dose treatment period with vortioxetine followed by a 26-week, randomized, Double Blind, fixed-dose, placebo-controlled relapse-prevention period.

The study population will include *de novo* patients as well as rollover patients from other paediatric vortioxetine studies (Studies 12709A and 12712A), who, in the investigator's opinion, could benefit from continued treatment with vortioxetine. To reach 80 randomized patients, approximately 150 patients recruited, either as *de novo* patients or rollover patients from Study 12709A and 12712A, are estimated to be enrolled into the study.

De novo patients

- Patients meeting eligibility criteria for *de novo* patients will be enrolled in the 12-week, open-label, flexible-dose treatment period.

Rollover patients from Study 12709A (enrolled to the Open Label Period)

- Patients may participate in the present study after completion of the randomized, 8-week, Double Blind, placebo-controlled treatment period of Study 12709A.
- Eligible patients will be enrolled in the 12-week, open-label, flexible-dose treatment period.
- The Baseline Visit of this study (Study 13546A) will take place at the same visit as Visit 12 (Completion Visit) of Study 12709A. Participation in Study 12709A is considered completed when all assessments required at Visit 12 are completed.

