12.2 General Methodology for Other Safety Data

Unless otherwise specified, tables, graphs and listings will be based on the APES (Open Label Period) and the APRS (Double-Blind Treatment Period).

All tables and graphs will be presented by inclusion source (Open Label Period) and treatment group (Double-Blind Treatment Period).

All safety endpoints will be reported for the 12-week Open Label Period and the 26-week Double-Blind Treatment Period separately.

The denominators for the summaries of a given variable will be based on the number of patients with non-missing values at a given visit or during the assessment period.

Descriptive statistics for the safety variables, both absolute values and changes from baseline, will be presented by visit and for the last assessment. All available post-baseline assessments (including data collected at unscheduled visits) will be included in the identification of the last assessment. With respect to baseline, the definition as presented in [section 4.1](#) will be used.

The number and percentage of patients with at least one potentially clinically significant (PCS) value at any post-baseline assessment time point will be summarized by variable. All available assessments will be included in the evaluation of PCS values.

The number and percentage of patients with values out-of-reference range and/or PCS range will be summarized by variable, visit, and last post-baseline assessment.

For patients with post-baseline PCS values, listings will be provided including all the values for those patients for the variable, with flagging of PCS values and out-of-reference-range values.

The PCS values relating to the paediatric population in this study will be applied.

Lundbeck standard criteria for identifying PCS values will be used.

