12.5 Other Safety Endpoints

Tanner staging is a scale for assessing physical development and sexual maturity during onset and progress of puberty. The scale includes 5 stages of pubertal changes (called Tanner stages) separate for males and for females.

Data on Tanner staging and menstrual cycle (age of menarche, length of the menstrual cycle and menstrual cycle regularity) will be listed only.

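### Tanner stage and menstrual-cycle effects were to be summarized by treatment group under the protocol, but SAP 12.5 only lists them and gives no reason

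*SAP*

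**What the plan says.** **Endpoint definition.** The safety endpoints in protocol section 2 (Panel 4) are absolute values and changes from baseline in a list that includes "vital signs, height, weight, Tanner staging, electrocardiogram (ECG) parameter values". The same list stands in SAP Panel 1. Both add the short statement "Effects on menstrual cycle will be assessed".

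**Protocol analysis.** Section 16.8.10 says that "Tanner staging, and effects on menstrual cycle, vital signs, height, weight, BMI and ECG parameters will be summarized by treatment group". The synopsis also plans a summary: "Tanner staging, ECG, and effects on menstrual cycle, vital signs, height, weight, and ECG parameters will be summarized". Section 16.8.8 adds that "All safety endpoints will be reported for the 12-week open-label period and the 26-week double-blind period separately".

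**SAP analysis.** The general rule in SAP 12.2 is that "Descriptive statistics for the safety variables, both absolute values and changes from baseline, will be presented by visit and for the last assessment", with double-blind tables by treatment group. SAP 12.5 makes an exception. Its sentence on Tanner staging and the menstrual cycle, which names age of menarche first among the menstrual items, ends "length of the menstrual cycle and menstrual cycle regularity) will be listed only".

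**The concern.** The SAP replaces a by-arm summary with a listing for two endpoints that it still names in its own endpoint table. For Tanner stage it names a change from baseline but plans no tabulation of that change. Protocol 16.11 gives the SAP the job of describing the analyses in more detail; here it gives less, and does not mark the difference as a departure.

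The safety objective is long-term safety and tolerability, and the patients enter at 7 to 11 years. Protocol 9.4.7 describes Tanner staging as the measure of physical development and sexual maturity around puberty. The protocol adds a hormone panel, and the SAP tabulates it by arm, but the clinical stage recorded in the same children gets no table. Without a planned output, the clinical study report could meet the SAP and still omit a summary that the protocol promised.

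**Working it through.** The point itself is a comparison of texts. Arithmetic is needed only to see what a by-arm table would require.

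**1. Texts side by side**

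| Item | Protocol | SAP |
|---|---|---|
| Tanner stage as endpoint | Panel 4: absolute value and change from baseline | Panel 1: the same |
| Menstrual cycle as endpoint | Panel 4: effects to be assessed | Panel 1: the same |
| Planned output for both | 16.8.10: summary by treatment group | 12.5: listing only |
| Estradiol, LH, FSH | 16.8.10: summary by treatment group | 12.3: summary by treatment group |
| Height, weight | 16.8.10: summary by treatment group | 12.4, under the 12.2 rule: summary by treatment group |

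No other SAP section supplies a table for the two endpoints.

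**2. Are the data collected?** Yes. Protocol Panel 3 schedules Tanner staging and menstrual cycle at the Randomization Visit (Visit 8) and at Completion or Withdrawal (Visit 17). No new procedure is needed.

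**3. Which baseline would a table use?** SAP 4.1 sets the safety baseline at the start of the open-label period for *de novo* and 12709A patients, and at randomization for 12712A patients. For the first two groups, a change from that baseline includes 12 weeks of open-label vortioxetine, in the placebo arm too. The change would also be measured over different spans by inclusion source.

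**4. Would follow-up be equal?** No, because relapse means withdrawal (SAP 3.2). The inputs, from SAP 14, are relapse by Week 26 of 0.42 on vortioxetine and 0.69 on placebo, with 40 patients per arm. Assume constant hazards and no other dropout.

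- Hazard per week = −ln(1 − p)/26. Vortioxetine: 0.5447/26 = 0.02095. Placebo: 1.1712/26 = 0.04505.
- Mean weeks on study = p/hazard. Vortioxetine: 0.42/0.02095 = 20.1 (rounded up from 20.05). Placebo: 0.69/0.04505 = 15.3.
- Expected completers = 40(1 − p). Vortioxetine: 40 × 0.58 = 23.2. Placebo: 40 × 0.31 = 12.4.

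Pubertal stage advances with time, so a table of change to last assessment would tend to show more progression on vortioxetine from longer observation alone.

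**5. How precise would the table be?** The documents give no rate of stage advance, so a range is assumed. For a share p advancing at least one stage in each arm, the 95% half-width for the difference is 1.96 × √(2p(1 − p)/n).

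| Assumed p | n = 40 per arm | n = 20 per arm (one sex, if split evenly) |
|---|---|---|
| 0.05 | ±9.6 points | ±13.5 points |
| 0.10 | ±13.1 points | ±18.6 points |
| 0.20 | ±17.5 points | ±24.8 points |
| 0.30 | ±20.1 points | ±28.4 points |

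The normal approximation is rough at the low end (p = 0.05 with n = 20 is one child per arm), and the even sex split is an assumption. The table can describe the data but could detect only a large difference.

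**The case against.** A reader might infer that pubertal development is never compared between the arms. The documents do not support that. Estradiol, LH, FSH and prolactin are summarized by treatment group (SAP 12.3), as are height and weight (SAP 12.4 with 12.2). Tanner staging is done with the physical examination (protocol 9.4.7), and an abnormal examination finding judged clinically significant must be recorded as an adverse event (protocol 9.4.6). Treatment-emergent events are then tabulated by arm (SAP 12 and 12.1.7). A clinically important pubertal abnormality therefore has a route into a by-arm table. An ordinary difference in stage progression does not.

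A reader might also take the gap to cover two endpoints in all 80 randomized children. For the menstrual cycle it does not: cycle length and regularity exist only for girls past menarche, in patients enrolled below age 12. The documents give no sex split, so the size of this subset is unknown. The Panel 1 statement on the menstrual cycle also prescribes no table, so the conflict inside the SAP is clear only for Tanner stage. The conflict with protocol 16.8.10 holds for both.

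Two further arguments have some force. Listings carry treatment group, sex and age (SAP 6), so a reader could tabulate by hand; but that is not the promised summary. Sparse cells are a plausible reason for listing only; but the SAP does not give that reason, and it tabulates other safety data in the same patients. Finally, protocol 16.8.10 promises a summary without prescribing its layout. The layout under the fix is a proposal.

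**Conclusion.** The mismatch stands. Tanner stage and menstrual-cycle effects are stated safety endpoints with a promised summary by treatment group, and the SAP reduces both to listings without explanation. The consequence is limited to the missing descriptive by-arm summary of these two items. The hormone, growth and adverse-event summaries remain, and the primary analysis is untouched. This is a worthwhile small improvement. The conclusion that no by-arm summary is planned rests on the text alone. The caution about unequal follow-up rests on the plan's relapse rates, constant hazards and no other dropout.

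**What to change.** In SAP 12.5, add for the double-blind period:

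- a descriptive table by treatment group of Tanner stage, by sex, at the Randomization Visit and at completion/withdrawal, with the change between the two;
- a statement that this table uses the Randomization Visit as baseline in place of the SAP 4.1 open-label baseline;
- time on study by arm beside the table, or a completers-only version;
- counts by treatment group of menarche and cycle regularity among girls, with the number of girls as denominator.

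Keep the listing. If listing only is intended, state it as a departure from protocol 16.8.10 and give the reason.

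The cost is two small tables from data already scheduled. The downsides are sparse cells and a comparison affected by unequal follow-up. A completers-only version equalizes time but compares selected groups, about 23 and 12 patients under the planning assumptions, so it should be labelled descriptive.

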12.5.1 Columbia-Suicide Severity Rating Scale (C-SSRS) Scores

The C-SSRS was administered:

At screening using *the Baseline Screening version* to capture the baseline result (de novo patients only) and at every scheduled visit thereafter using the *Since last Visit version* to capture the C-SSRS assessments after baseline.

A summary capturing the patients with suicidal ideation, suicidal behaviour

The numbers and percentages of patients with baseline, or post-baseline suicide-related events based on the C-SSRS will be summarized. For the post-baseline assessments, the most severe score ([Panel 5](#)) per patient related to suicidal ideation and/or behaviour will be summarized.

The number and percentage of patients with no suicidal ideation or behaviour will be summarized. Patients in this category are those who:

answered 'no' to all ideation and behaviour questions; that is, answered 'no' to items in [Panel 8](#) related to suicidal ideation and answered 'no' to items related to suicidal behaviour.

Panel 5 C-SSRS Scores

C-SSRS Score	Related to:
Wish to be dead	Suicidal ideation
Non-specific active suicidal thoughts	
Active suicidal ideation with any methods (not plan) without intent to act	
Active suicidal ideation with some intent to act, without specific plan	
Active suicidal ideation with specific plan and intent	
Preparatory acts or behaviour	Suicidal behaviour
Aborted attempt	
Interrupted attempt	
Non-fatal suicide attempt	
Completed suicide (only applicable for the post-baseline assessments)	

The C-SSRS scores will be summarized per study period and by visit based on the APES (Open Label Period) or APRS (Double- blind Period) for patients with at least one post-baseline C-SSRS assessment in the respective period, regardless of whether they had a baseline C-SSRS assessment.

Missing C-SSRS scores will not be imputed.

Positive responses to *non-suicidal self-injurious behaviour* will be summarized separately.

For patients with any post-baseline suicidal behaviour (C-SSRS scores of 6 to 10), listings will be provided including all C-SSRS scores for those patients; C-SSRS scores related to suicidal behaviour will be flagged.

In addition, a listing with (highest) suicidal behaviour in the study or a period based on C-SSRS scores for those patients, and all SAEs related to suicidality, will be prepared.

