4.1 Definition of Baseline

The primary analysis of the study focuses on the results of the Double-Blind Treatment Period. Therefore, baseline for the primary analysis will be defined as the randomization visit, i.e. the start of the Double-Blind treatment period. This baseline will be referred to as Randomization (Visit).

For the analysis of safety, baseline is defined as the start of the Open Label Period for *de novo* and 12709A rollover patients. This baseline will be referred to as Baseline (Visit). For 12712A rollover patients baseline will be defined as the start of the Double-Blind Treatment Period, i.e. the randomization visit.

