4.2 Definition of Periods

The following periods can be identified:

Screening period

A Screening Visit will be performed only for de novo patients. Patients rolling over from Study 12709A will proceed directly to the Baseline Visit. Therefore, the screening period is not applicable for these patients. In addition, this period is not applicable for patients rolling over from Study 12712A, as these patients will enrol the study at the randomization visit. The screening period begins when the first screening assessment is done after written Informed Assent/Consent has been obtained, and ends at the Baseline Visit for the Open Label Period (visit 2).

Open Label Period

De novo patients who continue to meet all inclusion criteria and none of the exclusion criteria (see section 5.3 of the study protocol) will be enrolled into a 12-week Open Label Period. For patients rolling over from Study 12709A, the Baseline Visit of the Open Label Period will be performed the same day as the Week 12 (Completion) Visit of Study 12709A.

Patients eligible for entering the Open Label Period will start IMP (vortioxetine) at the Baseline Visit of the Open Label Period.

The duration of the Open Label Period is 12 weeks or until the patient is withdrawn from the study, whichever comes first. If a patient withdraws from the study, the Open Label Period ends at the withdrawal visit.

Double-Blind Treatment Period

The Double-Blind Treatment Period starts at the randomization visit (visit 8) and ends after 26 weeks of treatment (visit 17), or until the patient will be withdrawn from the study, whichever comes first. If a patient withdraws from the study the Double-Blind Treatment Period ends at the withdrawal visit.

Patients rolling over from Study 12712A will have their first visit in this study at visit 8 (the Randomization Visit). For 12712A-patients the last available values from assessments and procedures (efficacy/safety, and use of concomitant medication) performed at either Visit 7 (Week 8) and/or Visit 8 (Week 10), or Visit 9 (Week 12) in Study 12712A will be the Randomization Visit values for this study.

Safety Follow-up Period

The Safety Follow-up Period has a duration of 4 weeks after the last IMP intake. This period starts at the date of last IMP intake.

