12.5.2 General Behavior Inventory (GBI) 10-Item Mania Scale

The GBI 10-item mania scale is a parent- and patient-rated scale designed to screen for manic symptoms in children and adolescents. The ten items are rated on a 4-point scale from 0 (never or hardly ever) to 3 (very often or almost constantly). The total score ranges from 0 to 30, with higher scores indicating greater pathology. Only the parent-rated scale will be used in this study.

Summary statistics on the total score, absolute scores as well as changes from baseline for each visit as well as the latest assessment will be presented per study period and inclusion source (Open Label Period) and treatment group (Double-Blind Treatment Period).

13 Interim Analyses

No interim analyses will be performed.

14 Sample Size Considerations

The calculation of power is based on a log-rank test for the time to relapse at a one-sided 5% level of significance using SAS Proc Power. A sample size of 80 randomized patients (40 patients per treatment group) will provide at least 80% power to find a difference between vortioxetine and placebo as statistically significant, when expecting cumulative relapse rates at 0.42 and 0.69 over 26 weeks, respectively corresponding to a hazard-ratio of 2.15. The assumption of relapse rates (42% and 69% over 6 months for vortioxetine and placebo, respectively) is based on observed rates from a similarly designed relapse-prevention study of fluoxetine in pediatric patients with MDD who had an adequate response after 12 weeks of acute treatment¹.

It is anticipated that approximately 60% of *de novo* patients enrolled into the Open Label Period will qualify for the Double-Blind Treatment Period. To achieve 80 randomized patients, 150 patients are estimated to be enrolled into the study (depending on number and randomization rate of *de novo* and rollover patients).

15 Statistical Software

The statistical software used will be SAS[®], Version 9.4 or later.

16 Details on Data Handling

An LOCF approach will be used for the Double-Blind Treatment Period of the following scales: CDRS-R, PQ-LES-Q, CGI-I and CGI-S.

The LOCF approach will only be used for the total scores (if applicable). The last usable assessment in the Double-Blind Treatment Period (excluding the randomization assessment) will be used to impute missing values for the LOCF. See also section [Section 16.1.3](#) for the handling of missing data related to COVID-19.

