16.1 Assigning Data to Visits

16.1.1 Visit Window

The assessments at the scheduled visits will be used for the analyses. The assessment at the Withdrawal Visit for patients withdrawn from study will be assigned to a nominal visit in the Treatment Period, according to the visit windowing specified in [Panel 6](#). If the assessment at the Withdrawal Visit is assigned to the same visit as an assessment at a scheduled visit, the assessment from the Withdrawal Visit, which by definition always will be the latest, will be used.

Panel 6 Visit Windows

Nominal Visit Number	Nominal Visit Week	Nominal Visit Week (relative to randomization)	Nominal Visit Day	Time Window (days)	Mapping Window (days)
Open Label Period					
V1(screen)			-15	-5 to -15	
V2(baseline)	0	NA	0	-	
V3	1	NA	7	4 to 10	1 to 10
V4	2	NA	14	11 to 17	11 to 21
V5	4	NA	28	25 to 31	22 to 42
V6	8	NA	56	53 to 59	43 to 63
V7	10	NA	70	67 to 73	64 to 77
V8(end of Open Label Period)	12	NA	84	81 to 87	78 to 86
Safety follow-up (end of Open Label, for patients not entering Double-Blind Treatment Period)	16	NA	112	110 to 114	>86
Double-Blind Treatment Period					
V8(baseline of Double-Blind Treatment Period)	12	0	84	81 to 87	78 to 86
V9	13	1	91	88 to 93	87 to 95
V10	14	2	98	95 to 101	96 to 105
V11	16	4	112	107 to 117	106 to 119
V11, CGI-I only*	16	4	112	107 to 117	101 to 133
V12	18	6	126	121 to 131	120 to 140
V13	22	10	154	149 to 159	141 to 168
V13, CGI-I and PQ-LES-Q only*	22	10	154	149 to 159	134 to 182
V14	26	14	182	177 to 187	169 to 196
V15	30	18	210	205 to 215	197 to 224
V15, CGI-I and PQ-LES-Q only*	30	18	210	205 to 215	183 to 238
V16	34	22	238	233 to 243	225 to 252
V17	38	26	266	261 to 271	253 to 280
V18 - Safety follow-up (end of Double-Blind Treatment Period, for patients who completed the Double-Blind Treatment Period)	42	30	294	289 to 299	>281

*Different mapping for these variables only, due to a different schedule of assessments

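### As the SAP's baseline and period rules are written, a pre-randomization C-SSRS rating of de novo and 12709A children can enter the double-blind worst score in both arms (low severity)

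*SAP*

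**What the plan says.** **Safety baseline (SAP 4.1).** "For the analysis of safety, baseline is defined as the start of the Open Label Period for" de novo and 12709A rollover patients. The third source is treated differently: "For 12712A rollover patients baseline will be defined as the start of the Double-Blind Treatment Period, i.e. the randomization visit".

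**Scope of that baseline (SAP 12.2).** For the other safety data the text refers back to 4.1: "With respect to baseline, the definition as presented in" that section applies. The same section counts potentially clinically significant (PCS) values at any post-baseline time point.

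**Period (SAP 4.2).** "The Double-Blind Treatment Period starts at the randomization visit (visit 8) and ends after 26 weeks of treatment (visit 17"), or at withdrawal if that is earlier.

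**C-SSRS (SAP 12.5.1).** The screening rating is the baseline result for de novo children, and every later scheduled rating is described as coming after baseline. The most severe post-baseline score per patient is summarized. The tables are by period and by visit, on the APES or the APRS, "for patients with at least one post-baseline C-SSRS assessment in the respective period, regardless of whether they had a baseline C-SSRS assessment".

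**Visit windows (SAP 16.1.1, Panel 6).** Visit 8 has two rows with the same mapping window, days 78 to 86: "V8(end of Open Label Period") and "V8(baseline of Double-Blind Treatment Period").

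**Instrument (Protocol 9.4.10 and 8.4).** All ratings after screening use the since-last-visit form. For de novo and 12709A children, the Visit 8 safety assessments are made at the visit where the randomization criteria are checked.

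**The concern.** The double-blind C-SSRS table should describe what happened on randomized treatment. Under the rules above, ideation that a child reported for the last open-label weeks on vortioxetine could appear there as a double-blind finding, in the placebo column as well as the vortioxetine column.

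There are two further consequences. The table would mix two counting rules, because Visit 8 counts for two inclusion sources and not for the third. And a child rated at Visit 8 but never rated on double-blind drug would still qualify for the denominator.

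C-SSRS is a stated safety endpoint, and the population is children aged 7 to 11 on an antidepressant, so the table will be read closely even though no test is attached to it.

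**Working it through.** The plan states no figure on this point, so the check is mainly a reading of the rules together.

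**Step 1. Status of the Visit 8 rating**

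| Source | Baseline under 4.1 | Visit 8 post-baseline? | Visit 8 in Double-Blind Period (4.2)? | Scheduled ratings in worst score |
|---|---|---|---|---|
| De novo | Open-label start | Yes | Yes | Visits 8 to 17 = 10 |
| 12709A | Open-label start | Yes | Yes | Visits 8 to 17 = 10 |
| 12712A | Randomization visit | No | Yes | Visits 9 to 17 = 9 |

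If Visit 8 is the double-blind baseline for all, as Panel 6 labels it, every row has 9 ratings.

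**Step 2. Is there a rule elsewhere that settles it?** Two comparable rules exist, and neither covers C-SSRS. SAP 16 says "The last usable assessment in the Double-Blind Treatment Period (excluding the randomization assessment) will be used to impute missing values for the LOCF", but only for CDRS-R, PQ-LES-Q, CGI-I and CGI-S. SAP 12.1.4 counts double-blind TEAEs from the first double-blind dose, but only for adverse events.

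**Step 3. What the Visit 8 rating covers.** From Panel 6, Visit 7 is nominally day 70 (67 to 73) and Visit 8 day 84 (81 to 87).
- Nominal look-back: 84 − 70 = 14 days. Range: 81 − 73 = 8 to 87 − 67 = 20 days.
- Share of recall time for a completer (182 double-blind days): 14/(14 + 182) = 7.1%. Range: 8/190 = 4.2% to 20/202 = 9.9%.

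**Step 4. Which scores can carry over.** Protocol 5.5 requires withdrawal for ideation items 4 or 5 or suicidal behaviour. SAP 3.2 allows randomization only if no withdrawal criterion is met. That leaves ideation levels 1 to 3 in practice.

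**Step 5. Size.** With 40 children per arm, one child positive at Visit 8 and never again adds 1/40 = 2.5 percentage points. A child who is also positive later adds nothing to the count of positives.

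The documents give no ideation rate, no split by source and no overlap between ratings. The following is therefore an illustration under stated assumptions: a 26-week rate p of 5% or 15% spread evenly over 182 days, the same rate before randomization, all randomized children from the two affected sources, and independent ratings.
- Rate in the look-back: q = 1 − (1 − p)^(14/182). For p = 5%, q = 0.39%. For p = 15%, q = 1.24%.
- Newly positive per arm: 40 × q × (1 − p). For p = 5%: 40 × 0.0039 × 0.95 = 0.15. For p = 15%: 40 × 0.0124 × 0.85 = 0.42.
- With the longest look-back of 20 days and p = 15%: q = 1 − 0.85^(20/182) = 1.77%, and 40 × 0.0177 × 0.85 = 0.60.

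Fewer children from the affected sources, or overlap with later positive ratings, lowers these values, to zero with full overlap.

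**The case against.** The best defence is that a sensible reading exists. Panel 6 governs the assignment of data to visits and names Visit 8 the baseline of the Double-Blind Period. The reference in 12.5.1 to the respective period fits a period-specific baseline. The literal reading also leaves the eligibility clause almost no work, because nearly every randomized de novo or 12709A child would qualify through Visit 8 alone. In addition, SAP 1 places the table templates in a separate document, which may settle the layout.

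Much of this stands: Visit 8 as double-blind baseline is the better design choice and probably the intent. It does not remove the point. Panel 6 is a visit-window table, whereas 4.1 is the formal definition and 12.2 invokes it by reference. No text gives these two sources a randomization baseline for safety. The templates cannot be seen here.

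The defence on consequence is also largely right. The C-SSRS summary is descriptive (Protocol 16.8.10). Ideation levels 4 and 5 are to be reported as SAEs (Protocol 9.4.10), which are summarized by period under the first-dose rule. The by-visit table would still show Visit 8 separately. The primary endpoint, the efficacy analyses and the TEAE analyses are untouched.

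Finally, 12.2 applies the same baseline to PCS counts, so a change confined to C-SSRS would leave the other safety tables on a different rule. That is correct, and the fix covers both.

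**Conclusion.** The point holds as a low-severity clarification. The stated rules, if programmed as written, place a pre-randomization rating of de novo and 12709A children in the double-blind worst score and denominator. They exclude the same visit for 12712A children.

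The size cannot be computed from the documents. On the even-rate assumptions above it is about 0.15 to 0.6 newly positive children per arm, so likely under one.

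Two stronger conclusions are tempting and not supported:
- **That the table would be biased toward one arm.** The rating precedes randomization, and randomization is stratified by inclusion source, so the carry-over is the same in both arms in expectation. It can raise both rates and slightly dilute a true difference, but it does not set the direction.
- **That several children per arm would be misattributed.** A reader gets there by assuming, say, 10% positive at Visit 8. That would be twice an assumed 5% rate for the whole 26 weeks, within a look-back of about two weeks. These children have also just met the remission or response criteria at Weeks 10 and 12, and levels 4 and 5 have been removed. Nothing in the documents supports such a rate.

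**What to change.** In SAP 12.5.1, and in 12.2 for the counts of PCS values at any post-baseline time point, add a rule for Double-Blind Period summaries:
- Visit 8 is the pre-treatment value for all inclusion sources.
- Only assessments made after the first double-blind dose, including unscheduled and withdrawal visits, count as post-baseline for the worst score, the denominator and the listings.
- Visit 8 remains the last Open Label assessment for de novo and 12709A children.
- The 4.1 baseline for change-from-baseline summaries stays as it is.

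This mirrors the TEAE rule in 12.1.4 and agrees with the Panel 6 label. The cost is a sentence or two in each section and the matching programming and table templates. All the data are already collected.
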